11.4 Baseline/Pre-operative Assessment

All pre-operative procedures are to be completed prior to the study surgery. The Schedule of Events is listed in Table 1.

The pre-operative visit will include collection of basic demographic information, medical history, hip history and current use of prescription and over-the-counter pain medication and therapies.

The subject is to complete a series of surveys and scales regarding their clinical outcomes at the time preceding surgery, including pain, stiffness, function, and activities. These scales include:

- Numeric Pain Scale
- Modified Harris Hip Score
- Hip Outcome Score
- EQ-5D

For subjects enrolled after the completion of the Subchondroplasty Procedure, basic demographic information, medical history, hip history and pre-operative use of prescription and over-the-counter pain medication and therapies data should be collected, if available, from the subject's medical record or via patient interview. Pre-operative Numeric Pain Scale, Modified Harris Hip Score, Hip Outcome Score, and/or EQ-5D should **only** be entered if they were collected as part of the standard of care

11.5 Surgical Techniques

All operative procedures are to be performed under aseptic conditions according to the institution's standards and following the guidelines below.

- The pre-operative MRI should be used in planning the access point, trajectory and depth of the AccuPort cannula(s) for accessing the location of the subchondral bone defect(s).
- AccuPorts should be placed using fluoroscopic guidance.
- Appropriate volume of AccuFill should be used to adequately fill the area(s) of subchondral bone defect(s), per the recommended surgical technique guide, taking care not to over-pressurize or overfill the defect. Multiple fluoroscopic images should be taken during injection to check for extravasation of material.
- Any extravasation of material into surrounding soft tissues should be thoroughly irrigated at the time of the procedure.

The Investigator is to dictate detailed operative notes that include the measures listed below, or have paper copies of the Operative Details Case Report Forms completed during surgery to serve as source documents.

- Operative Details— Description of subject's operative procedure including such items as

OR time, SCP procedure time, anesthesia type, documentation of SCP injection, treated subchondral bone defect(s) (location and size), concomitant procedures and a device log (to include lot and product numbers).

- Adverse Event (if applicable) — Description of adverse events occurring during the operative procedure..

The patient will be considered a study subject after implantation of the study device.

If the AccuFill® is not able to be used during the surgery, the subject will be considered a screen failure and withdrawn from the study. The screen failure will not count against the site's total enrollment allotment.

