SAE	Serious Adverse Event
SADE	Serious Adverse Device Effect
UADE	Unanticipated Adverse Device Effect

4 Study Synopsis

Complete Protocol Title	A Longitudinal Outcomes Study of the Subchondroplasty® Procedure in the Hip
Protocol Number	CSU2017-03KC
Short Protocol Title	SCP Hip Outcomes Study
Sponsor	Zimmer Biomet, Warsaw, Indiana, United States
Manufacturer	Zimmer Biomet AccuFill® BSM ETEX Corporation [name] USA
Study Device(s)	AccuFill® Injectable Calcium Phosphate SCP® Surgical Instrumentation
Study Objectives/Endpoints	To collect data on the short- and long-term outcomes for subjects undergoing the Subchondroplasty® (SCP®) Procedure in the hip in a standard clinical setting. Outcomes to be assessed include medication usage, pain, function, activity levels and patient satisfaction.
Indications/Target Population	Candidates with at least one subchondral bone defect in the form of a cyst and/or bone marrow lesion (BML), insufficiency fracture or bone defect associated with early stage avascular osteonecrosis (AVN) in the femoral head, femoral neck and/or acetabulum who have elected to undergo or who have undergone the Subchondroplasty Procedure, will be enrolled in the study.
Inclusion/Exclusion Criteria	Candidates must meet ALL of the following: 
 1. Surgeon considers the patient appropriate for the SCP Procedure of the hip. 2. Subchondral bone defect(s) in the femoral head, femoral neck and/or acetabulum has been confirmed via radiographic finding on MRI or x-ray. 3. Subject provides voluntary signature on the IRB approved Informed Consent Form. 4. Subject is at least 18 years of age. 5. Subject must be physically and mentally willing and able, in the Investigator's opinion at the time of enrollment, to be compliant with the protocol and complete outcome forms via email, telephone, in-person or by regular mail.

	
Candidates will be excluded if they meet ANY of the following:
 
 1. Subject has collapse of subchondral bone. 2. Subject is pregnant at the time of surgery. 3. Subject is incarcerated. 4. Subject is involved in active litigation related to the condition being treated. 5. Subject is not comfortable with speaking, reading, and understanding questions and providing responses in an available language for the PROs in the protocol.
Study Design	This study is a post-market, single arm, non-randomized multi-center investigation.

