10.7.1 Primary Endpoint

The primary endpoint is defined by the overall group mean improvement from baseline of the Modified Harris Hip Score at the two year time point. The safety of the system will be assessed by monitoring the frequency and incidence of adverse events. Relation of the events to implant (Accufill®), instrumentation (SCP® Surgical Instrumentation) and/or procedure should be specified.

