11.3 Determination of Eligibility and Enrollment

Potential subjects will be screened from each Investigator's patient population to determine if they meet the inclusion criteria described in Section 7.1 and none of the exclusion criteria described in Section 7.2. Subjects will not be invited to participate in the study until after approval of the protocol by the reviewing IRB.

Subjects will be considered enrolled in the study if they meet the eligibility criteria, consent to participate in the Investigation and undergo the SCP Procedure where AccuFill is injected. Valid enrollment status is not granted until after surgery due to the possibility of intra-operative exclusions where the SCP Procedure does not occur. At the conclusion of the subject's surgery, the subject will be entered into the electronic database and a subject number will be generated.

Retrospective enrollment will only be allowed with prior written approval from the Sponsor after evaluation of pre-operative data available for potential retrospective subjects. The subject will sign an Informed Consent Form prior to completing follow-up study questionnaires.

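### Enrolment depends on AccuFill injection, so the plan does not ensure that instrument- or procedure-related harms in attempted but non-injected cases are counted or followed up

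*Combined protocol and SAP*

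**What the plan says.** **Who is a subject.** Section 11.3 counts a patient as enrolled on meeting the eligibility criteria, consenting, and going on to "undergo the SCP Procedure where AccuFill is injected". It gives the reason: "Valid enrollment status is not granted until after surgery due to the possibility of intra-operative exclusions where the SCP Procedure does not occur". At the end of surgery "the subject will be entered into the electronic database and a subject number will be generated". Section 11.5 adds that "The patient will be considered a study subject after implantation of the study device", and then: "If the AccuFill® is not able to be used during the surgery, the subject will be considered a screen failure and withdrawn from the study". Such cases do not count toward the site's allotment, and the synopsis states the target of about 50 as implanted subjects.

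**What safety covers.** The synopsis lists the study devices as "AccuFill® Injectable Calcium Phosphate SCP® Surgical Instrumentation". Under 10.7.1, "The safety of the system will be assessed by monitoring the frequency and incidence of adverse events", and "Relation of the events to implant (Accufill®), instrumentation (SCP® Surgical Instrumentation) and/or procedure should be specified".

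**What is recorded.** Section 10.4 has intra-operative safety events recorded at surgery, and 11.5 asks for a description of them. Table 1 makes the withdrawal form (CRF 10) and the adverse event form (CRF 11) available at Surgery. Section 12.4.4 requires an End of Study form for every consented subject who is withdrawn and keeps the data collected up to that point, unless the subject asks otherwise in writing.

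**What is analysed.** Section 16.3 summarises complications as counts and percentages. It names no safety set and no denominator.

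**The concern.** Section 7.1 places the drilling of the delivery cannula before the injection. One study device has therefore already been used on the patient when the event that confers subject status takes place. If the instruments fail or cause harm and the injection is abandoned, the patient leaves the study population because of an intra-operative outcome that a study device can produce. This is selection on a post-exposure outcome, and it bears on an endpoint that asks for attribution to that device.

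At stake is the adverse event incidence for the instrumentation and the procedure. With about 50 subjects, a few uncounted cases could change how the safety result reads. A harm that appears days after an abandoned attempt is the most exposed, because the recording routes above concern the operation itself.

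**Working it through.** **The plan's own figure.** The only sample-size figure is in 16.1, and this point does not depend on it. It reproduces: a two-sided one-sample t-test with difference 31.4 − 18.0 = 13.4, SD 22.4 and alpha 0.05 reaches 80% power at n = 24 (power 0.801), and 24/0.75 = 32. The question here is which patients are counted.

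**Following one patient through the text.** Take a consented patient in whom the cannula is drilled but AccuFill is not injected.

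1. *Status.* Screen failure, withdrawn, never enrolled (11.3, 11.5).
2. *Event seen in theatre.* It can be recorded on CRF 11 (10.4, 11.5, Table 1) and is kept (12.4.4). Whether a patient who is never enrolled receives a database entry and subject number is not stated, since 11.3 describes that step alongside enrolment.
3. *Event appearing later.* Section 11.7 requires post-operative data for enrolled subjects. No section provides adverse event follow-up for this patient.
4. *Device deficiency.* Section 13.1.7 asks that deficiencies be documented even where no adverse event followed. None of the twelve forms listed in Table 1 is named for that purpose.
5. *Attribution.* Section 12.4.9 limits reporting to events related to the device or procedure and defines the device as AccuFill alone. An instrument event is reportable only if it is read as procedural, whereas 10.7.1 wants the instrumentation identified.
6. *Summary.* Section 16.3 does not say whether the event enters the numerator or the patient the denominator.

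**Illustration of size.** The documents give no rate of non-injection. Assume 50 implanted subjects with no instrument- or procedure-related event, plus x attempted but non-injected cases, each with one such event. These cases come on top of the 50 because screen failures do not use up the allotment.

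- Implanted only: 0/50, with exact upper 95% limit 1 − 0.025^(1/50) = 7.1%.
- All attempted: rate = x/(50 + x), with exact (Clopper–Pearson) limits. With n = 50 + x, the lower limit is the 0.025 quantile of Beta(x, n − x + 1) and the upper is the 0.975 quantile of Beta(x + 1, n − x).

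| x | Events/attempted | Rate | 95% CI |
|---|---|---|---|
| 0 | 0/50 | 0% | 0 to 7.1% |
| 1 | 1/51 | 2.0% | 0.0 to 10.4% |
| 2 | 2/52 | 3.8% | 0.5 to 13.2% |
| 3 | 3/53 | 5.7% | 1.2 to 15.7% |
| 5 | 5/55 | 9.1% | 3.0 to 20.0% |

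The pattern does not depend on a zero count among implanted subjects. With one event in the implanted 50 (1/50 = 2.0%), x from 1 to 5 gives 2/51 = 3.9% to 6/55 = 10.9%. With two (2/50 = 4.0%), it gives 3/51 = 5.9% to 7/55 = 12.7%.

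The table does depend on every non-injected case having an event. If non-injected cases had events at the same rate as injected ones, the percentage would not move.

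**The case against.** The strongest reply is that the protocol does capture these cases. Intra-operative events have a form and a visit column, withdrawn consented subjects keep their data, procedure-related events go to the sponsor, and 13.1.7 points toward documentation. This stands as far as recording in theatre goes. A reader might infer from the withdrawal rule that such events are excluded from the safety endpoint, but the documents do not say so. They leave open whether the records are counted, and they provide no follow-up after the operation.

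A reader might also infer that instrument-related events in general are lost. They are not: events in injected subjects stay in the endpoint. Nor do the documents show that non-injection usually signals a device problem. AccuFill may go unused for unrelated reasons, and because 7.1 allows arthroscopy first, a case may end before any SCP instrument is introduced.

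The design also lowers the stakes. This is a descriptive, single-arm, post-market study of commercially available devices, the instruments are Class I and premarket exempt (6.3), no technical-success endpoint is defined, and no safety hypothesis is tested. An implanted cohort suits the score endpoints. The illustration is constructed, and even its 5.7% lies inside the 0 to 7.1% interval for 0/50. All of this is fair. However, that interval reflects sampling error among injected subjects and does not cover selection of who is included.

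Finally, retrospective enrolment (8, 11.3) admits only patients who have already had the procedure, so a simple attempted-case denominator over all enrollees would mislead. That objection is correct and shapes the fix.

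**Conclusion.** The point holds as a gap in the safety population. Subject status turns on successful injection, while a named study device acts before injection. The plan neither assigns attempted, non-injected cases to a safety denominator nor follows them for later harm, so instrument- or procedure-related harms in them may go uncounted.

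The size cannot be estimated from the documents. Under the stated assumptions (50 implanted subjects with no event, and 1 to 5 non-injected cases each with one), the rate would be 2.0% to 9.1% of attempted cases instead of 0%. With no such cases there is no effect. The sample size and the score endpoints are not affected.

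A reader might conclude that reported safety and performance will be overstated. The documents do not support that: they give no number of abandoned attempts, no event rate among them, and no statement that their events are left out of the summary. The change is still worth making, because it is cheap and removes a selection on an intra-operative outcome.

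**What to change.** - **11.3, 11.5 and 16.3:** define a safety set of all prospectively consented subjects in whom SCP instrumentation is introduced, whether or not AccuFill is injected, and make it the denominator for adverse event summaries. Subjects in whom no SCP instrumentation is used remain screen failures.
- **Data:** complete CRF 9 and CRF 11 for every member of this set, state that each receives a database entry, and collect adverse events through the first post-operative contact.
- **Reporting:** give the number not injected out of the number attempted among prospectively consented subjects only, and report retrospective enrollees separately.
- **Scores:** keep the implanted set for the Modified Harris Hip Score and the other score endpoints.
- **12.4.9 and 10.7.1:** reconcile the definition of the device as AccuFill alone with the endpoint's separate attribution to the instrumentation.

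The cost is a protocol amendment with IRB approval (section 20), a few extra forms and contacts, and possibly a slightly less favourable safety figure. The two named CRFs already exist.

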11.6 Surgical/Immediate Post-Operative Assessment

During the immediate postoperative period, the investigator's standard postoperative care procedures should be followed. A numeric pain score will be collected and all adverse events and complications are to be assessed and recorded on the Adverse Event Form, per Section 12.4.9 Adverse Events.

Rehabilitation should be performed per the investigator's standard of care.

11.7 Follow-up Procedures

In order to minimize the burden to patient and physician, patients will be enrolled at the physician's office, but will not be required to come back to the office for follow-up visits.

A Numeric Pain Score will be collected at the first post-operative standard of care visit at approximately 7-21 days.

Thereafter, subjects complete self-reported outcomes measures post-operatively at 6 weeks, 12 weeks, 6 months, 1 year and 2 years. These measures include:

- Use of pain medication and therapy
- Subject-reported outcomes:
 - Numeric Pain Scale
 - Modified Harris Hip Score
 - Hip Outcome Score
 - EQ-5D
 - Subject Global Satisfaction Survey

The post-operative visit data must be collected for each enrolled subject via email, in-person, regular mail or telephone (with an IRB approved phone script). If the subject is not seen in person, a member of the study staff will contact the subject by telephone at the aforementioned time points to inquire about their outcomes, any conversion surgeries, and adverse events.

Follow-up evaluations are detailed in Table 1— Schedule of Events. Follow-up is to occur within the windows described in Table 1.

The study database will be configured to send an email notification to subjects at the beginning of each specified visit window with a reminder that they need to complete the surveys. This email will contain a method to allow the subjects to complete their surveys electronically via the database's electronic Patient Reported Outcomes (ePRO) system.

Prior to contacting the study subject to assess potential adverse events by telephone, a member of the study staff will check to confirm whether these surveys have been completed electronically or not. If the subject has not completed the evaluation yet, a member of the study staff will ask if the subject would like to complete the questionnaires by phone, email or if they would like a copy of the surveys to be mailed out to them. Mailed surveys will be sent with a stamped, return envelope. The subject should be instructed to return the surveys within one week and to include the date of completion at the top of any of the pages. Any subject survey forms that are not collected via the database's ePRO system are to be maintained in the subjects' study files as source documents.

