Clinical Phase	Post-market
Sample Size	Approximately 50 study subjects implanted with the study device per cohort.
Length of Study	7 years (5 years of enrollment (all sites) and 2 years of follow-up)
Materials and Methods	Case report forms will be completed either in-office or hospital at Pre-op, Surgery, Discharge, and 6 weeks, 1-year, and 2-years.
Data Collection	Paper/Electronic
Statistical Reporting	Data collected will be summarized and reported to each participating investigator. Statistical analysis will be conducted by Zimmer Biomet or its designee.
Scores/Performance Assessments	
Pre-Operative
 
Initial study procedures include patient demographics, medical history and hip history. Additionally, the following measures will be obtained pre-operatively:
 
 • Use of pain medication and therapy • Subject-reported outcomes: 
 ○ Numeric Pain Scale ○ Modified Harris Hip Score ○ Hip Outcome Score ○ EQ-5D 
Subjects will complete only the Numeric Pain Scale at 2 weeks post-operatively.

	
Post-Operative
 
Thereafter, subjects complete self-reported outcomes measures post-operatively at 6 weeks, 12 weeks, 6 months, 1 year and 2 years. These measures include:
 
 • Use of pain medication and therapy • Subject-reported outcomes: 
 ○ Numeric Pain Scale ○ Modified Harris Hip Score ○ Hip Outcome Score ○ EQ-5D ○ Subject Global Satisfaction Survey 
The post-operative visit data must be collected for each enrolled subject via email, telephone, in-person or by regular mail. If the subject is not seen in person, a member of the study staff will contact the subject by telephone at the above time points to inquire about their outcomes, any conversion surgeries, and/or adverse events.

Standards	
The PMCF is compliant with the below:
 
 • ISO 14155: 2020 - Clinical investigation of medical devices for human subjects - Good clinical practice. • The Declaration of Helsinki (DoH) - Ethical principles for medical research involving human subjects. • European Regulation (EU) 2017/745
Study Funding	
Funding for this clinical study is made available by Zimmer Biomet to support clinical data collection, IRB/EC review fees and other expenses associated with the conduct and execution of this study protocol as outlined in the fully executed Clinical Trial Agreement.

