10.4 Study Design

This study is designed as a post-market, single arm, non-randomized multi-center investigation.

Male and female subjects, at least 18 years of age, with at least one subchondral bone defect in the form of a cyst and/or bone marrow lesion (BML), insufficiency fracture or bone defect associated with early stage avascular osteonecrosis (AVN) in the femoral head, femoral neck and/or acetabulum who are suitable candidates for use of AccuFill during the Subchondroplasty Procedure are eligible for enrollment in this study.

A maximum of 15 study sites, in the United States of America, will enroll a target of 50 subjects.

Each Investigator must obtain IRB approval, or favorable opinion by an EC, prior to consent of the first subject; no study-related procedures can occur without the approval and oversight of a registered IRB or EC. If the study site does not have an IRB of record, a central IRB may be utilized upon approval by Zimmer Biomet.

Demographics, medical history, hip history and use of pain medication and therapy will be recorded at the time of subject consent. Additionally, patient reported outcomes measures will be obtained pre-operatively. Operative details including the SCP Procedure, concomitant surgical procedures and intraoperative safety events will be recorded at the time of surgery. Prospective subjects will be considered enrolled in this study once their Subchondroplasty Procedure has been performed.

Subjects will complete only the Numeric Pain Scale at 2 weeks post-operatively. Thereafter, subjects will complete self-reported outcomes measures post-operatively at 6 weeks, 12 weeks, 6 months, 1 year and 2 years. These measures include information on pain medication and therapy, pain levels, function, activity and subject satisfaction. Screening for adverse events and conversion will occur throughout the study.

Subjects will complete the study at 2 years or will be withdrawn if they undergo conversion of the Subchondroplasty site. For the purposes of this protocol, a conversion will be defined as

total hip arthroplasty or any procedure involving removal of the AccuFill material on the index hip.

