11.9 Surgical Reoperation or Revision

A reoperation of the index hip or revision of the SCP injection site may be performed at the discretion of the Investigator (e.g., due to progressive pain or disability, etc.). A reoperation is defined as any surgical procedure on the index hip. For the purposes of this protocol, a revision will be defined as any partial or total joint arthroplasty or any fusion, bone fixation, bone grafting, or bone substitute procedure in the study hip.

If the reoperation occurs due to an adverse event, the event should be documented on a Serious Adverse Event Form and an Exit Form completed, and the subject exited from the study.

In the event that a revision occurs (defined as any partial or total joint arthroplasty or any fusion, bone fixation, bone grafting, or bone substitute procedure in the index hip), the subject will be exited from the study. A Serious Adverse Event Form and an Exit Form will be completed.

Use of any postoperative injections into the index hip should be recorded on the Medication Form at the next questionnaire completion window.

12 Reporting

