12.4.4 Subject Withdrawal

Study participation may be discontinued through surgical conversion (Total Hip Arthroplasty or total removal of AccuFill), withdrawal of consent, Investigator decision or death. A subject may voluntarily withdraw their consent from the study at any time without prejudice or affecting their future medical treatment. Investigators may withdraw a subject due to non-compliance with the protocol or follow-up questionnaire schedule, or for reasons of medical discretion.

All consented subjects who are withdrawn/ discontinued from the study should have an End of Study form completed to explain why they are no longer participating in the study.

When a subject withdraws or is withdrawn, all study procedures completed and data collected prior to the date of withdrawal will be submitted to the sponsor and included in the study database, unless the subject requests otherwise in writing.

Should a subject who previously chose to withdraw wish to re-enter the study, a new Informed Consent will be required. The site may resume scheduled follow-up visits from the subject's last follow-up visit.

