12.4.9 Adverse Events

An adverse event (AE) is defined as an untoward medical occurrence, unintended disease or injury, or untoward clinical signs (or change or worsening of a pre-existing medical condition) in a patient, which may or may not have an association with the device or procedure. In addition an adverse device effect is defined as ‘any untoward and unintended response to a medical device’.

Each Adverse Event Form should only include one adverse event. When reporting an adverse event, it is important to record the diagnosis rather than the symptoms, event or treatment. For example, a subject who undergoes a Total Hip Arthroplasty after the Subchondroplasty Procedure may have had the procedure due to increased pain caused by hip osteoarthritis. In this case, ‘Severe Osteoarthritis’ or something similar (as determined by the Investigator) should be recorded as the diagnosis rather than ‘Total Hip Arthroplasty’. Abbreviations/colloquialisms should also be avoided when recording the diagnosis.

For this study, **only AEs which are possibly or definitely related to the device or procedure will be reported to the sponsor**. The determination whether the AE is related to the device or procedure will be based upon whether a causal relationship between the device or procedure and the AE is at least a reasonable possibility, i.e., the relationship cannot be ruled out. A causal relationship cannot be ruled out if, in the medical judgment of the Investigator, the effect follows a reasonable temporal association with the use of the device.

For this study, device implies the AccuFill Bone Substitute Material and procedure implies the Subchondroplasty Procedure.

13 Safety Management – Medical Events/Adverse Events

Adverse events are required to be reported on the **Adverse Event Report** case report form. The completed **Adverse Event Report** case report form must be submitted to the Sponsor in a timely manner. The Investigator or Designee will also promptly provide the Sponsor with any additional requested information required for the Sponsor to comply with regulatory requirements. If applicable per their reporting requirements, the Investigator or Designee will also report applicable adverse event(s) to their IRB or EC.

The following definitions are from ISO 14155:2020.

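### The scheduled remote contact names only conversions among hip operations, while Section 11.9 also exits subjects for other revisions and for some reoperations, so some of these may be missed

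*Combined protocol and SAP*

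**What the plan says.** Section 11.7 does not require office visits after enrolment. If a subject is not seen in person, staff telephone at each time point to "inquire about their outcomes, any conversion surgeries, and adverse events". The synopsis (Section 4) has nearly the same words: "inquire about their outcomes, any conversion surgeries, and/or adverse events". Section 10.4 likewise limits ongoing screening to adverse events and conversion.

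The surgical terms are defined in several places:

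- Section 10.4: a conversion is "total hip arthroplasty or any procedure involving removal of the AccuFill material on the index hip", and it leads to withdrawal.
- Section 12.4.4: participation may end through "surgical conversion (Total Hip Arthroplasty or total removal of AccuFill"), which is narrower because removal must be total.
- Section 11.9: a revision is "any partial or total joint arthroplasty or any fusion, bone fixation, bone grafting, or bone substitute procedure in the study hip". Every revision leads to exit, with a Serious Adverse Event Form and an Exit Form.
- Section 11.9 also says: "A reoperation is defined as any surgical procedure on the index hip". A reoperation leads to exit if it is due to an adverse event.
- Section 12.4.8: participation ends on a revision that removes a study device, which is a further variant.

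On adverse events, Section 12.4.9 states that "only AEs which are possibly or definitely related to the device or procedure will be reported to the sponsor".

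**The concern.** The inquiry is narrower than the exit rule it has to serve. A subject followed only by e-mail and telephone could have a fixation, a grafting or a repeat bone substitute procedure, perhaps at another hospital, and truthfully report no conversion. Unless the operation comes up under another topic, the site may not learn of it.

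Two things are at stake. The first is the count of further hip surgery. Section 10.7 aims to confirm long-term safety and performance, and Section 10.7.1 sets safety monitoring beside the primary endpoint. The second is the primary mean: if a revision goes unnoticed and the subject still returns a 2-year Modified Harris Hip Score, that score is analysed although Section 11.9 would have ended participation first.

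**Working it through.** **Step 1. Set the definitions side by side.**

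| Operation on the index hip | Conversion (10.4)? | Exit under 11.9? | Asked about by name (11.7, synopsis)? |
|---|---|---|---|
| Total hip arthroplasty | Yes | Yes, as a revision | Yes |
| Partial arthroplasty, fusion, fixation, grafting or bone substitute procedure that removes AccuFill | Yes | Yes, as a revision | Yes |
| The same procedures with AccuFill left in place | No | Yes, whatever the cause | No |
| Other reoperation due to an adverse event, AccuFill left in place | No | Yes | No, only through the adverse-event topic |
| Other reoperation not due to an adverse event, AccuFill left in place | No | No | No |

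The third and fourth rows are the gap: exit events that the inquiry does not name. The fifth row matters for counting reoperations but not for exit.

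**Step 2. Check the other routes of detection.**

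- *Outcomes topic.* The measures listed in 11.7 cover medication and therapy, pain, function, EQ-5D and satisfaction. None is described as a surgery item, and Table 1 lists no revision or reoperation form.
- *Adverse-event topic.* This can bring an operation to light if the subject thinks of it as an adverse event. Section 12.4.9 asks for the diagnosis rather than the treatment, so a reported event need not name the operation.
- *Serious Adverse Event and Exit Forms (11.9, 12.4.2).* These are completed once the site knows of the surgery. They document it; they do not detect it.

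**Step 3. Under-count.** With about 50 subjects, each subject whose surgery is missed lowers the reported proportion by 1/50 = 2 percentage points. The documents give no hip reoperation rate, so the number missed cannot be estimated.

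**Step 4. Primary mean.** Section 16.1 supplies the planning values: mean improvement 31.4, SD 22.4, MCID 18.0, 80% power, alpha 0.05, 25% attrition. The plan's own figure comes first. A one-sample t-test with difference 31.4 − 18.0 = 13.4 and two-sided alpha 0.05 needs n = 24 (power 80.1%), and 24/(1 − 0.25) = 32. Both stated figures reproduce and are not in dispute.

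Now let a share f of the analysed hips be unrecognised revisions with mean gain g, the rest gaining 31.4. The documents give neither f nor g, so both are assumptions. Section 16.1 plans for one year, so using 31.4 at two years is also an assumption.

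Mean = (1 − f) × 31.4 + f × g, so the shift is f × (g − 31.4).

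| f | g = 0 | g = 31.4 | g = 45 |
|---|---|---|---|
| 5% | −1.57 | 0 | +0.68 |
| 10% | −3.14 | 0 | +1.36 |
| 20% | −6.28 | 0 | +2.72 |

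For scale, 50 × 0.75 = 37.5, so about 37 hips would be analysed, and 5% of 37 is about 2 hips. The sign depends wholly on how revised hips score.

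**The case against.** The strongest reply is that Section 11.7 lists topics, not questions. Telephone collection uses an IRB-approved script, and neither the script nor the case report forms are in the documents; they may ask more. Outcomes and adverse events are raised at every contact. The relatedness limit in 12.4.9 governs what reaches the sponsor, not what the site hears. Its threshold is low, since a relationship need only be impossible to rule out, and 13.2.2 counts unassessable cases as possible. Its worked example treats arthroplasty for osteoarthritis as arising from an adverse event. Exit for a revision does not depend on relatedness, and 11.9 and 12.4.2 expect the Investigator to be involved in the decision.

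Much of this stands, and it rules out several stronger readings that a reader might infer:

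- *That these operations are not asked about at all.* They are not asked about by name; other topics may bring them out.
- *That no partial arthroplasty, fusion or grafting is a conversion.* One that removes AccuFill is a conversion under 10.4.
- *That every reoperation requires exit.* Under 11.9 a reoperation that is not a revision requires it only if due to an adverse event.
- *That revised hips stay in the 2-year mean.* This needs every route to fail and the subject to return a 2-year score. A detected revision is exited.
- *That both effects favour the device.* Missed surgery does understate the failure count. For the mean, Step 4 shows the sign is open, and removing failed hips could itself flatter the result.

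What the reply does not supply is a statement in the protocol that staff should ask about index-hip surgery other than conversion. Investigator involvement does not guarantee knowledge of surgery done elsewhere.

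**Conclusion.** The point holds in limited form. Followed as written, the remote inquiry and the screening statement do not expressly cover all the operations that lead to exit under 11.9, so their ascertainment is not assured and further hip surgery may be under-counted. A missed revision may also leave a score in the primary mean; the size and direction of that effect cannot be determined from the documents, and the table in Step 4 is illustration only. Reoperation is not a named endpoint, and nothing here disputes the sample size. The conclusion assumes that the phone script follows the protocol wording; a script that already asks about any hip surgery would leave only the protocol text to align. The change is worth making because it is cheap and follow-up may be entirely remote.

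**What to change.** In Section 11.7, the synopsis and Section 10.4, replace the reference to conversion surgeries or conversion with *any surgery on the study hip since the last contact (date, hospital, type)*. Ask it at every contact, whatever the cause. Have the site, not the subject, classify each answer as conversion, revision or reoperation, and update the IRB-approved phone script to match.

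Separately, the wordings on conversion, revision and exit in Sections 10.4, 11.9, 12.4.4 and 12.4.8 disagree and must be reconciled so that the classification has one reference. Which exit rule applies is for the sponsor and investigators. The new question improves detection under any of them.

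The cost is a short IRB script update and a few more operations for sites to classify.
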